This is a Phase III, prospective, longitudinal, mixed-methods RCT designed to test the efficacy of the MSM Intervention in lung cancer surgery. The use of an attention control condition as the comparison group will minimize the potential for Hawthorne's effect. Building from our previous work and based on the Chronic Care Self-Management Model (CCM), the MSM Intervention is a nurse-led, caregiver-based, telehealth, multimedia care model for lung cancer surgery. Its primary focus is to provide support for FCGs on their post-operative caregiving role and managing their QOL needs through goal setting, proactive planning, and building self-management and problem-solving skills. The MSM Intervention also supports caregiver-patient dyads in preparing for surgery and self-management during post-operative recovery at home. The MSM Intervention includes video, handbook, and post-discharge telephone support. It is administered at five time points: before surgery, during hospitalization, and at Day 2, Day 7, and 2 months post-discharge. It utilizes both in-person encounters as well as telephone for intervention administration.

Endpoints:

Primary:

Family Caregivers: Burden, Caregiving Preparedness, Psychological Distress, QOL, Cancer support services use

IRB 17238 02/02/2023

Patients: Psychological distress, QOL, Healthcare Resource Use (home health nursing care, urgent care/ER visits, readmissions)

Outcome Mediators: Activation, Self-Efficacy, Surgery-Related Knowledge

Secondary:

Moderators of FCG/patient outcomes and reciprocal relationships

Additional Studies:

Geriatric Assessment for FCGs and patients

Social determinants of health

Spiritual Well-Being

Sample Size:

200 family caregiver-patient dyads (400 participants total)

Estimated Duration of the Study

60 months

Summary of Subject Eligibility Criteria:

Inclusion Criteria:

Family caregiver: 1) A family member or friend identified by the patient as being the primary care provider before and after surgery; 2) A patient/care recipient enrolled in the study; 3) Age 21 years or older; 4) Able to read or understand English or Chinese.

Patient: 1) Diagnosis of lung cancer or presumed lung cancer (as determined by surgeons); 2) Scheduled to undergo surgery for treatment; 3) A family caregiver enrolled in the study; 4) Age 21 years or older; and 5) Able to read or understand English or Chinese.

Investigational Product Dosage and Administration:

Not Applicable

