	Family Caregiver Activation in Transitions (FCAT) Tool	х	X	х	x			
Outcome Mediators	Patient Activation Measure (PAM)	X	Х	х	х			
Mediators	Self-Efficacy Scale	х	X	х	х			
	Surgery-Related Knowledge Tool	х	х	х	х			
	Sociodemographic and Health Status	х						
Exploratory	STS General Thoracic Surgery Data Collection Form				x			
	Exit Interview Discussion Guide				x			
	RN Debriefing Form	After each intervention session						
Process	Intervention Fidelity Checklist	1st five participants and every 10th session thereafter						

Family Caregivers:

Distress Thermometer (DT) – The DT is an efficient, low subject burden measure to evaluate psychological distress over the past week, based on a scale of 0 (no distress) to 10 (extremely distressed). According to the National Comprehensive Cancer Network (NCCN), psychological distress is defined as mixed anxiety and depression symptoms. ⁹⁸ A cut-off of 3/10 indicates a need for intervention, with acceptable sensitivity (94.1%) and specificity (71.2%) compared to

IRB 17238 02/02/2023

the Hospital Anxiety and Depression Scale (HADS).⁷¹ The DT has been validated in FCGs, with receiver operating characteristics (ROC) of 0.88 relative to the HADS.^{71, 99} It is also validated in lung cancer patients.⁷⁰

Montgomery Borgatta Caregiver Burden Scale (MBCBS) – This 14-item tool was designed to measure the impact of caregiving on three dimensions of burden: objective, subjective demand, and subjective stress. Internal consistency for the three dimensions ranges from .81 to .90. The ordinal scale ranges from 1-5 (a lot less to a lot more). The following cutoff scores are interpreted as high burden: 1) a score of 23 or > for objective burden, 2) a score of 15 or > for subjective demand, and 3) a score of 13.5 or > for subjective stress.

Preparedness for Caregiving Scale – This is an 8-item scale of the Family Care Inventory by Archbold and colleagues. ¹⁰¹ Items are scored from 0 to 4, with higher scores indicating better preparedness. A mean score is tabulated for all items. Internal consistency ranges from 0.88 to 0.93. ^{102, 103}

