For this hypothesis, we will address patient psychological distress and QOL. Distress and QOL are each quantitative scales measured at both 1 month and 3 months. These will be analyzed by the same plan described for Specific Aim 1, hypothesis 1.1 and 1.2. Each analysis will be a repeated measures ANCOVA statistical design, removing variances prior to examining mean squares for the group by occasion interactions, and covarying the baseline scores. The independent variable will be group (intervention vs. attention control).

Hypothesis 2.2: The intervention group will have lower in-home nursing care, lower urgent care/ER visits, and lower hospital readmissions.

Similar to Specific Aim 1, hypothesis 1.3, patient healthcare resource use will be evaluated by recording in-home nursing care, urgent caregcp/ER visits, and readmissions (COH and non-COH encounters). Each subject will be classified as having an event or not. There is no baseline value, but the data will be tabulated by surgery stratum, and tested for homogeneity (interaction) before estimating and testing overall treatment effect.

Specific Aim 3: Test the effects of the MSM Intervention on outcome mediators at discharge and 3-months post-discharge, comparing intervention and attention control groups. **Hypothesis 3.1:** FCGs and patients in the intervention group will experience higher activation, self-efficacy, and knowledge.

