For this hypothesis, we will address outcome mediators, including FCG and patient activation, self-efficacy, and knowledge. These outcomes are each quantitative scales measured at both 1 month and 3 months. These will be analyzed by the same plan described for Specific Aim 1 & 2. Each analysis will be a repeated measures ANCOVA statistical design, removing variances prior to examining mean squares for the group by occasion interactions, and covarying the baseline scores. The independent variable will be group (intervention vs. attention control). In addition, we will use structured equation modeling (SEM) to evaluate whether a mediator accounts for all or part of the effect between treatment and outcome. We will focus on the following: 1) estimating how treatment affects mediators, 2) how mediators are associated with outcomes, and 3) estimating, at least roughly, the relative strengths of mediation by activation, self-efficacy, and knowledge, as well as direct effects on outcomes. Each FCG model will involve variables describing: intervention (treatment assignment), 3 mediational variables (1month activation, self-efficacy, knowledge), baseline values of 3 mediational variables, and primary outcomes (baseline values and 1-month). Intervention effect on patient outcomes is also proposed to be mediated by activation, self-efficacy, and knowledge. Each patient model will involve 11 observed variables: intervention (treatment assignment), 3 mediational variables (1month activation, self-efficacy, knowledge), baseline values of 3 mediational variables, and primary outcomes (baseline values and 1-month).

Exploratory Aim 1: Explore moderators (age, sex, marital status, caregiver relationship to patient, caregiver employment status, co-morbidities) of FCG and patient outcomes and reciprocal relationships.

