We will use semi-structured interviews to examine dyadic experiences with the MSM Intervention. Qualitative data will be analyzed by the PIs using the conventional content analysis approach. This approach is used to describe a phenomenon where existing theory or research literature is limited. Data from the tape-recorded interviews will be transcribed and analyzed using HyperRESEARCHTM qualitative software. Transcripts will be imported allowing for the development of analytic categories, data coding, and review of coded data. All data will be read repeatedly to achieve immersion and obtain a sense of the whole. Then, data will be read word by word to derive codes. Codes will then be sorted into themes based on links and relationships. Separate investigators with experience in qualitative data analysis ([name] and [name]) will conduct a final validation review of the codes and themes to ensure consistency and clarity across all qualitative data. Data discordantly coded will be discussed for refinement and consensus purposes.

Geriatric Assessment (GA) data for both FCGs and patients will be analyzed descriptively. We will use descriptive statistics (mean [SD], median [range], percentage [95% confidence interval]) to summarize GA scores and domains. We will also describe the patterns of changes in GA over time for both FCGs and patients. Changes will be calculated as post-surgery scores minus pre-surgery scores. Exploratory logistic regression models (univariate and multivariate) will be fitted to study the correlation between GA and FCG/patient outcomes.

COVID-19 qualitative data will be analyzed using content analysis approaches as described under exploratory aim 2.

Social determinants of health (SDH) data will be scored according to guidelines descriptively summarized. We will use multiple linear regression to test associations between baseline outcomes and SDH predictors. Baseline scores of outcomes activation, burden preparedness, self-efficacy, QOL and distress will be summarized with descriptive statistics. Distributions of SDH predictors will be summarized. For each outcome, we will use bivariate regression to assess the effect of one predictor at a time. Stepwise multivariate analysis will be performed to select all significant predictors (p<0.05). In addition, multicollinearity issues will be examined by calculating correlation matrix for all predictors and by checking variance inflation factors.

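### The exploratory geriatric assessment analysis names logistic regression for outcomes that are mostly quantitative scores, with no cut-point assigned; linear or ordinal models would keep information that dichotomising discards

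*Combined protocol and SAP*

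**What the plan says.** The GA paragraph stands in Section 13.1, after Exploratory Aim 2. It opens with "Geriatric Assessment (GA) data for both FCGs and patients will be analyzed descriptively" and then gives its only inferential method: "Exploratory logistic regression models (univariate and multivariate) will be fitted to study the correlation between GA and FCG/patient outcomes". It does not say which outcomes are meant, at which visit, whether GA is predictor or response, whether the model is binary or ordinal, or where a score would be cut.

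Elsewhere the plan is clear about what these outcomes are:

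- The Synopsis endpoints for caregivers are "Family Caregivers: Burden, Caregiving Preparedness, Psychological Distress, QOL, Cancer support services use". For patients they are distress, QOL and healthcare resource use.
- On patient distress and QOL, E.5 (Aim 2) says "Distress and QOL are each quantitative scales measured at both 1 month and 3 months". On the mediators (activation, self-efficacy, knowledge), Aim 3 says "These outcomes are each quantitative scales measured at both 1 month and 3 months".
- Only the use outcomes are binary. For these E.5 states "Each subject will be classified as having an event or not".
- The social determinants (SDH) paragraph, close after the GA one, takes baseline activation, burden, preparedness, self-efficacy, QOL and distress as outcomes and says "We will use multiple linear regression to test associations between baseline outcomes and SDH predictors".

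Section 12.1.3 describes cut-offs for some instruments. For the Distress Thermometer (DT), "A cut-off of 3/10 indicates a need for intervention"; objective burden counts as high from 23. It gives no cut-off for preparedness or COH-QOL-Family, and for FACT-L only a 2 to 3 point important difference for the subscales. None of these is tied to the GA analysis.

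**The concern.** On the natural reading, a method for binary responses has been named for a set of outcomes that are mostly scores. Six of the eight items in the Synopsis list of caregiver and patient endpoints are scores, as are six of the nine rows in Tables 3 and 4. Adding the three mediator rows of Table 5 makes it nine of twelve.

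To fit a binary logistic model to a score, the analyst must cut it. That has two costs. Information within each side of the cut is discarded, so real associations are more easily missed. And because no cut is assigned, it could be chosen after the data are seen, so the result could depend on that choice.

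The data are not cheap. Section 5.6 puts GA questionnaire completion at 27 minutes for patients, and the Study Calendar schedules GA three times for patients and twice for caregivers.

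**Working it through.** **Planning inputs.** The documents give no power or precision figure for the GA models, so there is no stated figure to reproduce. The check borrows the Table 3 means and SDs, so I first confirmed that the table is coherent. With 80 per group, power = Φ(difference / (SD × √(2/80)) − 1.96):

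- Caregiver DT: 1.2 / (2.6 × 0.1581) = 2.92, power 83.1% (stated 83%).
- Objective burden: 1.8 / (4.0 × 0.1581) = 2.85, power 81.2% (stated 81%).

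**Information kept after a cut.** For a normal score and a weak association, the efficiency of the dichotomised score relative to the intact one is φ(c)² / [p(1−p)]. Here c is the cut in SD units from the mean and p = Φ(c). Normality is my assumption.

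| Cut | c | Kept | Lost | Equivalent n of 160 |
|---|---|---|---|---|
| Median | 0 | 63.7% | 36.3% | 102 |
| Caregiver DT at 3 (mean 3.7, SD 2.6) | −0.27 | 62.0% | 38.0% | 99 |
| Caregiver DT at 2.5 | −0.46 | 58.9% | 41.1% | 94 |
| Caregiver DT at 3.5 | −0.08 | 63.5% | 36.5% | 102 |
| Objective burden at 23 (mean 22.0, SD 4.0) | 0.25 | 62.2% | 37.8% | 100 |
| 30/70 split | 0.52 | 57.6% | 42.4% | 92 |
| 20/80 split | 0.84 | 49.0% | 51.0% | 78 |

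The DT is shown at 2.5 and 3.5 because a cut-off of 3 on a whole-number scale can include or exclude a score of 3. The median split gives the smallest loss for a normal score. The 160 is the number of dyads Section 13.1 expects to retain at 3 months.

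**Power, as an illustration.** Assume a correlation r = 0.20 (not in the documents), n = 160 and a two-sided 0.05 test. By Fisher's z, power ≈ Φ(atanh(r) × √157 − 1.96), with √157 = 12.53. Cutting multiplies r by φ(c)/√[p(1−p)].

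- Intact score: 0.2027 × 12.53 = 2.54, power 72%.
- Median split: r becomes 0.20 × 0.798 = 0.160; 0.1610 × 12.53 = 2.02, power 52%.
- Top 25%: r becomes 0.20 × 0.734 = 0.147; 0.1478 × 12.53 = 1.85, power 46%.

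**Check with logistic models.** In 2,000 simulated samples of 160 per cut, with r = 0.219 so that the correlation test had about 80% power, binary logistic regression had 61% power at a median split, 57-59% with the cut about 0.25 SD from the mean, and 49% at 20/80.

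**The case against.** A reader might infer that the plan is bound to dichotomise, or that a fixed share of the information is certain to be lost. The documents support neither. Three other readings are open:

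- The models may cover only the yes/no outcomes. Hypotheses 1.3 and 2.2 name five event types, and Tables 3 and 4 carry three yes/no rows. For these, logistic regression is right and nothing is lost.
- The models may be ordinal. A proportional-odds model on 11 equally filled categories keeps about (3/π) × (1 − 1/121) = 95% of the information (an approximation).
- A GA impairment category may be the response, since the sentence gives no direction and Section 5.6 quotes cut-offs for several GA instruments.

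The linear SDH model could likewise mean that logistic regression was chosen on purpose for a different kind of outcome. Published cut-offs also have a clinical reading, so a cut there is not arbitrary. And E.4 anticipates transformations and floor and ceiling effects, so normality is approximate at best.

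All of this stands against a claim of certain loss. It does not remove the point. Section 5.1 and Exploratory Aim 1 list outcomes that are mainly or wholly these scores, and the GA sentence carries no restriction. Under any of these readings the plan still has to state the outcomes and the model form. The published cut-offs are not assigned here, and several of the scales have none.

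**Conclusion.** The point holds as a minor one. As worded, the GA analysis applies logistic regression to outcomes that are mostly scores, with no cut-point assigned, while the SDH analysis keeps largely the same scores quantitative.

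If the scores are cut, the loss is at least about 36% for a roughly normal score and a weak association. It is about 36-41% near the DT and objective burden cut-offs and about 51% at a 20/80 split. Because no cut is stated, no single figure can be given; skewed or bounded scores would change these values, and the correlation of 0.20 is illustrative. The loss does not apply to the yes/no outcomes.

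A reader might also infer harm to the trial's main conclusions. The documents do not support that: the regressions are labelled exploratory, the main GA analysis is descriptive, and no primary test or sample size rests on them.

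**What to change.** Reword the GA sentence in Section 13.1 to:

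- use linear (or ordinal) regression for distress, burden, preparedness, QOL and FACT-L, adjusting for the baseline score when the outcome is post-baseline (a cross-sectional baseline analysis has no such covariate);
- keep binary logistic regression for social work referral, family resource center use and patient healthcare resource use;
- name the outcomes, their visit, and whether GA is predictor or response;
- make any analysis at the instruments' published cut-offs secondary, with the cut-offs stated in advance.

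This costs a sentence or two. It needs no new data, visits or participants, and leaves the primary analyses untouched.

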
(Table 5). Standard deviations (SD) were estimated from previous data. For activation, an improvement of the mean by 8.0 points could be detected with 80% power. For self-efficacy, an improvement of 2.0 points could be detected

IRB 17238 Packet: 26 with 80% power. For knowledge, a difference of 5.0 points can be detected with 88% for 80 dyads per group.

Sample Size and Power Calculation for Social Determinants of Health and Spiritual Well Being – Sample size calculation is based on linear multiple regression method using

G*power (Version 3.1.9.4). This method tests the null hypothesis that the proportion of variance of the outcome explained by a set of predictors is zero (i.e., $R^2=0$), while the alternative hypothesis is $R^2>0$. Significance level is 0.05 and power is 0.8. 20% of attrition was considered in calculation.

Two parameters need to be specified for sample size calculation⁷⁴: effect size and number of predictors. The effect size is the ratio of proportion of variance explained by a set of predictors and error variance⁷⁴. Since there is no published data for correlation between our outcomes and predictors in the target population (lung cancer), and due to the exploratory nature of the analyses, the effect sizes are estimates only. To cover

Effect size Number of predictors 0.15 0.25 0.35 137 87 65 14 162 104 80 19 184 119 92

132

102

203

24

Table 2. Sample size considering 20% attrition

potential effect sizes that our data may reveal, we employed different levels of effect size defined by Cohen⁷⁵: small 0.15, medium 0.25, and large 0.35. The total number of predictors is 24 for FCG arm and 23 for patient arm. However, some predictors come from the same SDH domain, thus they would be highly correlated. To avoid multicollinearity in multiple regression model, some predictors may be removed from the final model. Therefore, we also used different number of predictors to calculate sample size (**Table 2**). Assuming the effect size 0.35 and 20% attrition, our target sample size will be 51 dyads (102 total participants) to detect deviation of R² from zero with 0.05 significance level and 80% power.

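### The social-determinants analysis is sized on an overall R-squared test that the analysis section does not specify, and it instead selects predictors stepwise at p<0.05

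*Combined protocol and SAP*

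**What the plan says.** The sample-size paragraph for SDH and spiritual well-being (protocol section 13.1) describes one test per regression: "This method tests the null hypothesis that the proportion of variance of the outcome explained by a set of predictors is zero", against the alternative that it exceeds zero. The settings are "Significance level is 0.05 and power is 0.8" and "20% of attrition was considered in calculation". The effect sizes (explained over error variance) are "small 0.15, medium 0.25, and large 0.35". On predictors it says "The total number of predictors is 24 for FCG arm and 23 for patient arm", adds that those from the same SDH domain would be highly correlated, and allows that "some predictors may be removed from the final model". At effect size 0.35 it concludes "our target sample size will be 51 dyads (102 total participants"). The paragraph calls the analyses exploratory.

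The SDH paragraph of E.5 plans multiple linear regression to test associations between SDH predictors and baseline activation, burden, preparedness, self-efficacy, QOL and distress. It names three steps: a bivariate regression for each predictor and outcome; then "Stepwise multivariate analysis will be performed to select all significant predictors (p<0.05"; and, in addition, a correlation matrix and variance inflation factors. It does not name an overall F or R-squared test, the direction of the stepwise procedure, a multiplicity rule, or any validation or shrinkage.

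**The concern.** The hypothesis used for sizing and the inference described are different things. The sizing asks whether the predictor set as a whole explains anything, with one 5% error rate per outcome. The analysis asks which individual predictors cross p<0.05 after a search. A search over many candidates crosses that line by chance far more often than 5% of the time, and the p-values and confidence intervals of the survivors take no account of the search. A reader of the results could also attach the stated 80% power to the selected predictors, although it was calculated for something else. What is at stake is over-interpretation of SDH associations in the eventual report. No treatment comparison depends on it.

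**Working it through.** **1. Reproduce the plan's sample size.** Inputs from section 13.1: alpha 0.05, power 0.80, f² = 0.35, k = 24 predictors, 20% attrition. The power of the overall F test is P(F′ > F crit), with degrees of freedom k and n − k − 1 and noncentrality f²·n. Raising n until power reaches 0.80 gives n = 85. Then 85 × 1.20 = 102, the stated total. The same method gives:

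| k | f² = 0.15 | 0.25 | 0.35 |
|---|---|---|---|
| 9 | 137 | 87 | 65 |
| 14 | 162 | 104 | 80 |
| 19 | 184 | 119 | 92 |
| 24 | 203 | 132 | 102 |

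This matches the plan's whole table (the label of its first row is lost in the text; 9 is inferred because it fits). So the powered test is the overall F test in one regression. Attrition was added as n × 1.2; dividing by 0.8 would give 85 / 0.8 = 106.25, that is 107.

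**2. False selection when nothing is related to the outcome.** Forward selection keeps at least one predictor exactly when the smallest one-predictor p-value is below 0.05. For independent candidates the chance is about 1 − 0.95^k:

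- k = 24: 70.8%
- k = 23: 69.3%
- k = 19: 62.3%
- k = 14: 51.2%
- k = 9: 37.0%

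The plan expects correlated predictors, so this was simulated with normal predictors in blocks of five. The block size and the correlations are assumptions. Results are per outcome, at n = 41 and 51:

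| Candidates | r = 0 | r = 0.5 | r = 0.8 | Overall F test |
|---|---|---|---|---|
| 24, forward | about 70% | about 63% | about 50% | about 5% |
| 9, forward | about 37% | about 31% | about 23% | about 5% |

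For 24 candidates the forward rates are nearly the same at n = 85 and hardly change at 102 (checked there with 23 candidates), so a larger sample does not cure the problem. The plan does not say whether selection is forward or backward. Backward elimination gave 75% to 79% with 24 candidates (2.0 to 3.4 noise predictors kept on average) and 37% to 42% with 9. An F test computed on the forward-selected model is no remedy: in the simulation it was significant whenever anything had been selected.

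**3. Repetition over outcomes.** By Table 2 of section 12.1.3, burden and preparedness are caregiver measures, so there are six outcomes for caregivers and about four for patients. With independent predictors, the chance of at least one false selection somewhere lies between the fully correlated and fully independent cases for the outcomes:

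- Caregivers: 71% to 1 − 0.292^6 = 99.9%.
- Patients: 69% to 1 − 0.307^4 = 99.1%.

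**4. Power of the overall F test if models are fitted by role.** The 102 is reached by adding 51 caregivers and 51 patients, but predictors are counted separately by role. At f² = 0.35:

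| n in the regression | k = 24 | 23 | 19 | 14 | 9 |
|---|---|---|---|---|---|
| 51 | 39% | 41% | 50% | 63% | 77% |
| 41 (about 51 × 0.8) | 24% | 26% | 34% | 46% | 62% |

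No predictor count in the plan's table reaches 80% at these sizes.

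**The case against.** The defence has several fair points.

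- **It is exploratory.** SDH is listed under additional studies in the synopsis, uses baseline data only and is separate from the randomised comparison. That stands and keeps the point minor. It does not correct p-values after selection or carry the 80% power over to them.
- **The 70% needs about 24 weakly correlated candidates.** This also stands. The plan itself expects high correlation within domains and possible removal of predictors. A reader might infer that stepwise selection will usually produce a false finding whatever the set. For a single outcome that fails with 9 candidates, and with 24 highly correlated ones forward selection is about an even chance.
- **The overall test is not ruled out.** A reader might infer that it will never be run. The documents support only that it is not specified: multiple linear regression is planned, software prints an overall F, and section 13.1 states the null hypothesis.
- **Every predictor gets an estimate anyway.** The bivariate step does supply unselected, unadjusted estimates. The adjusted results still come from selection.
- **The group sizes are uncertain.** SDH and the outcomes are both baseline, so loss to 41 may not occur. Section 5.6 also allows retrospective survey invitations, so 51 need not be a ceiling. The false-selection rate barely depends on n; the power figures do.
- **The overall F test would itself be underpowered by role.** This is correct, and it has to be stated with the fix.

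**Conclusion.** The concern holds in a limited form. The plan sizes the SDH work on an overall R-squared test, does not specify that test in the analysis, and relies on p<0.05 stepwise selection. That selection has a per-outcome false-selection rate of about 50% to 70% (forward, 24 candidates) or roughly 22% to 38% (forward, 9 candidates), against about 5% for the overall test. These rates assume that no predictor matters and use normal predictors with block correlations of 0 to 0.8.

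Two stronger readings are not supported. One is that many of the reported determinants will be false. That share depends on how many real effects exist, whereas the simulations assume none and the plan's own effect size of 0.35 implies R² = 0.35 / 1.35 = 0.26. The other is that switching to the overall F test would restore 80% power. That needs n = 85 in one regression with 24 predictors; with 51 people per role it is about 39%. This is a cheap improvement to an exploratory analysis, not a threat to the trial's main conclusions.

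**What to change.** In the SDH paragraph of E.5:

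1. Move the correlation and VIF checks first, and reduce the predictors by those checks alone, without looking at any outcome.
2. Fit that fixed set for each outcome and role.
3. Report the overall F test of R-squared = 0 as the inferential test.
4. Give all coefficients with 95% CIs, labelled hypothesis-generating.
5. Delete the stepwise p<0.05 selection.

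In section 13.1, say whether the regressions are pooled or fitted by role, and restate power for the number of people and predictors in each regression. By role with 51 people and f² = 0.35 this is about 39% (24 predictors), 41% (23) or 77% (9), and less if people are lost.

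The cost is wording and a little analysis time, with no new data or participants. The downsides are longer tables, a less sparse final model and a less favourable stated power.
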